8.10 Serious Adverse Events

A serious adverse event (SAE) is an AE that:

- Results in death
- Is life-threatening (see below)
- Requires hospitalization or prolongation of an existing hospitalization (see below)
- Results in a persistent or significant disability or incapacity (see below)
- Results in a congenital anomaly or birth defect

- Additionally, important medical events that may not result in death, be life-threatening, or require hospitalization may be considered SAEs when, based on appropriate medical judgment, they may jeopardize the subject and may require medical or surgical intervention to prevent any 1 of the outcomes listed above in this definition. Examples of such events include allergic bronchospasm requiring intensive treatment in an emergency room or at home, blood dyscrasias, or convulsions that do not result in hospitalization, or development of drug dependency or drug abuse.

Life-threatening refers to immediate risk of death as the event occurred per the reporter. A life-threatening experience does not include an experience, had it occurred in a more severe form, might have caused death, but as it actually occurred, did not create an immediate risk of death. For example, hepatitis that resolved without evidence of hepatic failure would not be considered life-threatening, even though hepatitis of a more severe nature can be fatal. Similarly, an allergic reaction resulting in angioedema of the face would not be life-threatening, even though angioedema of the larynx, allergic bronchospasm, or anaphylaxis can be fatal.

Hospitalization is official admission to a hospital. Hospitalization or prolongation of a hospitalization constitutes criteria for an AE to be serious; however, it is not in itself considered an SAE. In absence of an AE, a hospitalization or prolongation of a hospitalization should not be reported as an SAE by the participating investigator. This is the case in the following situations:

- The hospitalization or prolongation of hospitalization is needed for a procedure required by the protocol.
- The hospitalization or prolongation of hospitalization is part of a routine procedure followed by the center (e.g., stent removal after surgery). This should be recorded in the study file.
- A hospitalization for a preexisting condition that has not worsened.

Disability is defined as a substantial disruption in a person's ability to conduct normal life functions.

If there is any doubt about whether the information constitutes an SAE, the information is treated as an SAE.

8.11 Other Reportable Information

Certain information, although not considered an SAE, must be recorded, reported, and followed up as indicated for an SAE. This includes:

- **Pregnancy exposure to a test article:** Information about pregnancy exposure includes the entire course of pregnancy and delivery, and perinatal and neonatal outcomes, even if there are no abnormal findings. Both maternal and paternal exposures are considered other reportable information. For exposure involving the female partner of a male subject, the necessary information must be collected from the subject, while respecting the confidentiality of the partner.

- Lactation exposure to a test article with or without an AE.
- Overdose of a test article as specified in this protocol with or without an AE.
- Inadvertent or accidental exposure to a test article with or without an AE.

8.12 Overdose

Any administration of omadacycline of greater than 100 mg intravenously or 300 mg orally within a 24-hour period will be an overdose, regardless of whether the overdose is intentional or accidental, it is a reportable event and the sponsor must be notified within 1 business day. The site personnel will retain this confirmation report.

The physician managing the overdose may order any test he/she thinks is necessary to manage the subject properly.

8.13 Medication Errors

Medication errors are the result of administration or consumption of the wrong product, by the wrong subject, at the wrong time, and/or by the wrong administration route, due to human error.

Medication errors include, but are not limited to, the following:

- The administration and/or consumption of test article that has not been assigned to the subject
- Administration of expired test article

All AEs and SAEs must be handled as specified in this protocol whether or not they are associated with a medication error. A medication error associated with an SAE (including overdose, inadvertent exposure, and/or accidental exposure) will be reported with the SAE on the SAE Report Form. All other medication errors will be reported by e-mailing the Other Reportable Events Report Form as indicated in the Emergency Contacts (see [Section 2](#)).

8.14 Recording and Reporting

A subject's AEs and SAEs will be recorded and reported from the signing of the ICF/assent to the time of the Study Completion visit. The investigator must instruct the subject and his/her parent/LAR to report AEs and SAEs during this time period. Reports of death within 30 days after the last contact with the subject will be reported to the sponsor and additional information relative to the cause of death will be sought and documented.

All AEs and SAEs must be recorded on source documents. All AEs and SAEs for subjects who receive a treatment assignment will be recorded in the eCRFs.

The investigator must follow-up as medically necessary on all AEs and SAEs until the events have subsided, the condition has returned to Baseline, or in case of permanent impairment, until the condition stabilizes.

Adverse events should be based on the signs or symptoms detected during the physical examination and on clinical evaluation of the subject. In addition to the information obtained from those sources, the subject should be asked the following nonspecific question: "How have you been feeling since your last visit?" Whenever possible, AEs should be reported as a diagnosis rather than individual signs and symptoms. If a definitive diagnosis is not possible, the individual signs and symptoms should be recorded using standard medical terminology.

If an AE requires a surgical or diagnostic procedure, the illness leading to the procedure should be recorded as the AE, not the procedure itself.

Death should be recorded in the eCRF as an outcome of an AE. Any unanticipated risks to the subjects must be reported promptly to the IRB/IEC/REB.

8.14.1 Serious Adverse Event Reporting

All SAEs and follow-up information must be reported within 1 business day or 24 hours as required by local regulations by emailing a completed SAE Report to the email address below.

Serious Adverse Event (SAE) contact information:
E-Mail: [REDACTED]

8.14.2 Assessment of Relatedness

The investigator will assess causality (i.e., whether there is a reasonable possibility that test article caused the event) for all AEs and SAEs. The relationship will be characterized using the following classification:

- Not related: This relationship suggests that there is no association between test article and the reported event. The event can be explained by other factors such as an underlying medical condition, concomitant therapy, or accident, and no plausible temporal or biologic relationship exists between test article and the event.
- Related: This relationship suggests that a definite causal relationship exists between test article administration and the AE, or there is a reasonable possibility that the event was caused by the study medication, and other conditions (concurrent illness, progression/expression of disease state, or concurrent medication reaction) do not appear to explain the event.

Adverse events and SAEs also will be assessed for their potential relationship to the protocol. A protocol-related AE is one that is not related to the test article but is considered by the investigator or the medical monitor (or designee) to be related to the research conditions, i.e., related to the fact that a subject is participating in the study. For example, a protocol-related AE may be an untoward event related to a medical procedure required by the protocol.

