5 INVESTIGATIONAL PLAN

5.1 Overall Study Description

This is a Phase 1, open-label, multi-center study in children and adolescent subjects (males and females, 8 to < 18 years of age) with suspected or confirmed bacterial infections who are receiving concomitant systemic antibacterial therapy. This study will consist of 2 age cohorts:

- Cohort 1 (adolescents): 12 to < 18 years of age
- Cohort 2 (children): 8 to < 12 years of age

The study will consist of a Screening period of up to 48 hours prior to dosing, a single dose of study drug on Day 1 and a Study Completion Visit between Days 4 to 7.

Subjects will undergo screening evaluations to determine eligibility within 48 hours prior to dosing. Approximately 40 subjects (20 per age cohort) will be enrolled.

On Day 1, per Principal Investigator (PI) discretion, subjects will receive a single dose of either intravenous or oral omadacycline. For those receiving intravenous omadacycline, a 100 mg IV dose (in 100 mL normal saline solution) infused over 30 minutes at room temperature will be administered. For those receiving oral omadacycline, a single dose of 300 mg oral omadacycline tablet (150 mg tablet x 2) will be administered.

Oral study drug will be administered in the morning in a fasted state with no food or drink except for water at least 6 hours prior to dosing. Fasting is defined as no food, antacids, or multivitamins containing multivalent cations (e.g., aluminum, magnesium, calcium, bismuth, iron, or zinc) or drink except water for at least 6 hours before dosing. Subjects will have no food or drink except water for at least 2 hours after dosing and no dairy products, antacids, or other aluminum- or calcium-containing products (e.g., vitamins, supplements) for 4 hours after dosing.

A total of 7 blood samples for PK analysis for oral omadacycline and 8 blood samples for iv omadacycline will be collected at specified time points prior to dosing and through 48 hours after dosing. Safety assessments will include monitoring of adverse events (AEs), clinical laboratory test results, vital sign measurements, and physical examination findings.

Subjects will complete a Study Completion visit 4 to 7 days after dose completion. This visit may be performed via telehealth with subject's parent/legal authorized representative (LAR) to review ongoing medications and adverse events if the subject has already been discharged from the hospital before Day 4.

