9.1 Adverse Events

An adverse event (AE) is defined as any untoward medical occurrence associated with the use of a drug in humans, whether or not considered drug related.

The incidence of treatment-emergent AEs will be presented by treatment and total, within each cohort, system organ class, and preferred term according to the Medical Dictionary for Regulatory Activities (MedDRA), relationship to the study drug, and severity. Any serious adverse event (SAEs) and AEs leading to discontinuation of study drug will also be presented in a data listing.

A treatment-emergent AE (TEAE) is defined as any event not present before exposure to study drug or any event already present that worsens in intensity or frequency after exposure.

A serious adverse event (SAE) is defined as any AE that results in any of the following outcomes:

- Death
- Life-threatening
- Requires hospitalization or prolongation of an existing hospitalization (see below)
- Results in a persistent or significant disability or incapacity (see below)
- Results in a congenital anomaly or birth defect
- Additionally, important medical events that may not result in death, be life-threatening, or require hospitalization may be considered SAEs when, based on appropriate medical judgment, they may jeopardize the subject and may require medical or surgical intervention to prevent any 1 of the outcomes listed above in this definition. Examples of such events include allergic bronchospasm requiring intensive treatment in an emergency room or at home, blood dyscrasias, or convulsions that do not result in hospitalization, or development of drug dependency or drug abuse.

The AE's relationship to study treatment will be evaluated by the investigator. The following relationships will be collected on electronic Case Report Form (eCRF): related and not related.

The severity of AEs will be classified as mild, moderate and severe.

Adverse Events will be coded by system organ class (SOC) and preferred term (PT) according to MedDRA, version to be delineated in the CSR.

An overview of AEs will be presented by treatment and total, including number and percentage of subjects with any:

- Any TEAE
- Any treatment-related TEAE
- Any moderate TEAE
- Any treatment-related moderate TEAE
- Any severe TEAE

- Any treatment-related severe TEAE
- Any SAE
- Any treatment-related SAE
- Any TEAE leading to early discontinuation
- Any death

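### Protocol 8.14.2 contradicts itself on relatedness, and its two categories leave some adverse events with no valid code

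*Protocol*

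**What the plan says.** Protocol 8.14.2 has the investigator judge causality for every AE and SAE, and opens with one question: "whether there is a reasonable possibility that test article caused the event". It then provides two categories.

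- *Not related* has two parts joined by a conjunction. The first is "The event can be explained by other factors such as an underlying medical condition, concomitant therapy, or accident". The second is "and no plausible temporal or biologic relationship exists between test article and the event".
- *Related* is met by a definite causal relationship, "or there is a reasonable possibility that the event was caused by the study medication", followed by the further condition that "other conditions (concurrent illness, progression/expression of disease state, or concurrent medication reaction) do not appear to explain the event".

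SAP 9.1 leaves the judgement to the investigator and fixes the values: "The following relationships will be collected on electronic Case Report Form (eCRF): related and not related". Neither document gives a third category, a tie-break or central adjudication of drug relatedness. Protocol 12.1 requires relationship to test article to be determined before database lock, so the field cannot be left open.

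The population is described in Protocol 5.1 as subjects "with suspected or confirmed bacterial infections who are receiving concomitant systemic antibacterial therapy". Inclusion criterion 3 in Protocol 6.2 also admits subjects for whom such therapy is planned.

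Relationship to study drug is part of a named safety endpoint (SAP 3.2.2.1). SAP 9.1 uses it in four overview rows (treatment-related TEAE, moderate TEAE, severe TEAE and SAE), in the table of related TEAEs and in the listing of treatment-related AEs.

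**The concern.** With only two permitted values, the two definitions should cover every event, and they should agree with the question they are meant to answer. They do neither. Each category is written as a conjunction, and the second condition in each excludes the same event: one plausibly linked to omadacycline that also has an apparent other cause. The alternative causes named in the *Related* definition (illness, its progression, other medication) are present in these subjects by eligibility. AEs are collected only up to a visit 4 to 7 days after a single dose (Protocol 8.14 and 9.3), so post-dose events fall close to dosing in time.

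An investigator with such an event must still enter one of two values. The lead question points one way and the extra condition in *Related* points the other. If sites resolve this differently, the treatment-related counts for those events reflect the resolution as well as the drug. The ambiguity also reaches the protocol-related category in 8.14.2, which is open only to events not related to the test article.

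**Working it through.** The documents give no figure for relatedness, so there is none to reproduce. The check is logical, followed by the arithmetic of one event.

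**Conditions, all from Protocol 8.14.2**

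- D: a definite causal relationship exists.
- P: a plausible link, or reasonable possibility, exists.
- O: another factor appears to explain the event.

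**Definitions**

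- *Not related* = O and not P.
- *Related*, reading A = D or (P and not O).
- *Related*, reading B = (D or P) and not O. The punctuation allows either reading.
- Lead question = P.

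**Every combination (D implies P)**

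| D | P | O | Not related? | Related, A? | Related, B? | Lead question |
|---|---|---|---|---|---|---|
| 0 | 0 | 0 | no | no | no | not related |
| 0 | 0 | 1 | yes | no | no | not related |
| 0 | 1 | 0 | no | yes | yes | related |
| 0 | 1 | 1 | no | no | no | related |
| 1 | 1 | 0 | no | yes | yes | related |
| 1 | 1 | 1 | no | yes | no | related |

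Three results follow.

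1. Plausible and otherwise explained (row 4) fits neither category under either reading. The lead question answers related.
2. Not plausible and not otherwise explained (row 1) also fits neither. The lead question answers not related.
3. Definite with an apparent other cause (row 6) is *Related* under reading A and fits neither under reading B.

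The table treats a plausible link and a reasonable possibility as the same condition. If a plausible link is the weaker of the two, row 4 is unchanged, because a reasonable possibility still implies a plausible link. Events with a plausible link but no reasonable possibility would then fit neither category as well.

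The lead question used alone puts every row in exactly one category.

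**Size of one event**

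- Planned cell: 10 subjects per treatment and age cohort (Protocol 12.2); 2 × 2 × 10 = 40.
- One subject whose only candidate events fall in the gap: 1/10 = 10 percentage points in that cell. If the overview, which SAP 9.1 describes by treatment and total, pools the two cohorts, the step is 1/20 = 5 points.
- Sites: 40/15 ≈ 2.7 subjects per site, too few to separate a site's coding habit from its patients.

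**Outer limits under assumed gap counts.** The documents give no frequency. Assume k of 10 subjects have only row 4 events and nobody else has a related event. Exact Clopper-Pearson 95% intervals are added for scale; the SAP plans only counts and percentages.

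| k (assumed) | All coded not related | All coded related |
|---|---|---|
| 1 | 0/10 (0–31%) | 1/10 (0.3–45%) |
| 2 | 0/10 (0–31%) | 2/10 (3–56%) |
| 3 | 0/10 (0–31%) | 3/10 (7–65%) |
| 5 | 0/10 (0–31%) | 5/10 (19–81%) |

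These are limits. A cell probably spans several sites, and mixed coding would fall between the two columns.

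**The case against.** The strongest reply is that 8.14.2 does state its governing test in the lead question, and that the category texts only describe that judgement in soft language. On that view an investigator asks whether a reasonable possibility exists, answers, and the gap closes. This would work if the section said so. Instead it says the relationship will be characterized by the classification, and the classification adds a condition that the question lacks. Neither document says which prevails.

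A second reply is that an alternative cause must appear to explain the event; its mere presence is not enough. This stands, and it limits the point. A reader might infer that a child on another antibiotic who vomits two hours after dosing could not be coded *Related*. The text does not go that far. Subjects must be in stable condition, those who cannot tolerate oral medication are excluded from oral dosing, and a TEAE must be new or worsened. An investigator could reasonably find that nothing else appears to explain that event.

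A third reply is that safety evaluation does not rest on relatedness. This is correct. All TEAEs, TEAEs by severity, serious TEAEs and TEAEs leading to discontinuation are tabulated without it, as are laboratory and vital-sign changes. The sponsor team reviews safety on an ongoing basis (Protocol 12.5), and no formal comparison uses relatedness (Protocol 12.10).

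Finally, Protocol 11 says that eCRF instructions and AE reporting procedures are reviewed with investigators before enrolment. Those instructions might contain a rule, but they are not in the documents, and neither the protocol nor the SAP refers to one.

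**Conclusion.** The defect is real and textual. The section gives two different tests, and its categories are not exhaustive under either reading of the *Related* definition. It affects the four treatment-related overview rows, the related-TEAE table and the treatment-related listing, and only for events that fall in the gap. The step is 10 percentage points per affected subject in a planned cell of 10. That these events are likely is inferred from the eligibility criteria; no frequency is given.

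Three stronger conclusions are tempting, and the documents do not support them:

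- **The treatment-related rate is biased low.** A site following the extra condition in *Related* would code *Not related*. A site following the lead question, or noticing that *Not related* is unavailable, would code *Related*. No direction can be established.
- **Each site's default decides the safety result.** Site coding behaviour is undocumented, and most safety summaries do not use relatedness.
- **Relatedness is the only means of judging drug effect in this uncontrolled study.** The summaries named above do not depend on it.

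A correction is worth making: the rule feeds a named endpoint, cannot code events this population makes likely, and is cheap to repair.

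**What to change.** In Protocol 8.14.2, state that the lead question alone decides:

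- *Related*: there is a reasonable possibility that the test article caused the event, whether or not another cause could also explain it.
- *Not related*: there is no such reasonable possibility.

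Remove the conflicting clauses from both definitions, or make them considerations that inform the answer to the lead question. Put the same rule in the eCRF completion guidance and refer to it in SAP 9.1. This closes both gaps and settles the definite-with-other-cause case.

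Optionally, record the alternative cause in a separate eCRF field, so that related events with and without a competing explanation can still be told apart.

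The cost is an amendment to the wording, an eCRF note and, if wanted, one field. The downside is that the treatment-related count may rise, possibly noticeably, and becomes less specific to omadacycline. The optional field offsets the loss of specificity.

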8.14.3 Assessment of Severity

The severity (or intensity) of an AE will be classified using the following criteria:

- Mild: These events are usually transient, require minimal or no treatment, and do not interfere with the subject's daily activities.
- Moderate: These events result in a low level of inconvenience or concern with the therapeutic measures. Moderate events may cause some interference with normal functioning but pose no significant or permanent risk of harm.
- Severe: These events interrupt a subject's usual daily activity and may require systemic drug therapy or other treatment. Severe events are usually incapacitating.

Changes in the severity of an AE should be documented as a new event to allow an assessment of the duration of the event at each level of intensity to be performed.

8.14.4 Laboratory Findings

Protocol-defined safety laboratory test results will be analyzed as part of specific laboratory safety analyses. Additional laboratory test results at other time points may be available to the investigator as part of standard clinical practice. Throughout the study, laboratory-related abnormalities should be recorded as AEs only if considered clinically significant, outside the range of expected values given the subject's Baseline assessments and clinical course, and not known to be part of another AE diagnosis.

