8.9 Adverse Events

An AE is any untoward, undesired, or unplanned event in the form of signs, symptoms, disease, or laboratory or physiologic observations occurring in a person given a test article or in a clinical study. The event does not need to be causally related to the test article or clinical study. An AE includes, but is not limited to, the following:

- Any clinically significant worsening of a preexisting condition.
- An AE occurring from overdose of a test article, whether accidental or intentional. Overdose is a dose greater than that specified in the protocol.
- An AE occurring from abuse (e.g., use for nonclinical reasons) of a test article.
- An AE that has been associated with the discontinuation of the use of a test article.

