9.2 Clinical Laboratory Tests

All laboratory testing will be performed by the local laboratory at each site. The relevant local laboratory results from Screening will be used to assess eligibility as per the inclusion/exclusion criteria.

The following laboratory tests will be performed:

Hematology	Hematocrit, Hemoglobin, Mean cell volume, WBC count, Platelet count, White blood cell differential, Neutrophils, Lymphocytes, Monocytes, Eosinophils, Basophils
Serum Chemistry	Blood glucose, Urea, Creatinine, Sodium, Potassium, Chloride, Bicarbonate, ALT, AST, AP, Total bilirubin, Total protein, Albumin, CK, Calcium, Phosphate, Cholesterol, Uric Acid, GGT, Amylase, Lipase

SARS-CoV-2 Sample	Molecular testing for SARS-CoV-2 will be performed at the local laboratory using an upper respiratory sample (e.g. nasopharyngeal swab or saliva) collected either at Screening or upon current hospital admission. Test results from this sample are not required before a subject is enrolled
Pregnancy Assessment	Females of reproductive potential (post-menarchal or has reached Tanner Stage 3 breast development) will have a local laboratory urine or serum pregnancy test at Screening.

ALT = alanine aminotransferase, AP = alkaline phosphatase, AST = aspartate aminotransferase, CK = creatine phosphokinase, GGT = gamma-glutamyl transpeptidase

The hematology, Serum Chemistry, SARS-CoV-2 sample, and pregnancy assessment tests will be performed at the timepoints indicated in the schedule of events (SOE). The schedule of events can be found in [Section 11](#).

Clinical laboratory test results will be presented in data listings. Actual results and changes from Baseline in clinical hematology and serum chemistry will be summarized by treatment within each cohort ,and time point. Shift from baseline in terms of low/normal/high for hematology and serum chemistry tests, and in terms of normal/abnormal will be summarized by treatment within each cohort and time point.for the safety population.

All laboratory data will be presented in data listings.

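### SAP 9.2's laboratory shift tables cannot show same-direction worsening in a child already abnormal at Baseline; if the change is also judged expected under Protocol 8.14.4, no planned incidence or shift category counts it

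*Protocol*

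**What the plan says.** **When a laboratory value becomes an AE.** Protocol 8.14.4 sets three joint conditions. The abnormality is recorded "only if considered clinically significant, outside the range of expected values given the subject's Baseline assessments and clinical course", and it must not belong to another AE diagnosis. No numeric threshold or toxicity grade is given. For everything else the section points to a separate route: "Protocol-defined safety laboratory test results will be analyzed as part of specific laboratory safety analyses".

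**How an AE is defined.** Protocol 8.9 includes laboratory observations, says "The event does not need to be causally related to the test article or clinical study", and lists "Any clinically significant worsening of a preexisting condition" as an example. Protocol 8.3 asks for any change in health status after consent to be reported as an AE. SAP 9.1 defines an AE as "any untoward medical occurrence associated with the use of a drug in humans, whether or not considered drug related", and its definition of a treatment-emergent AE (TEAE) takes in "any event already present that worsens in intensity or frequency after exposure". Cause is assessed under Protocol 8.14.2.

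**How laboratory data are analysed.** SAP 9.2 plans "Shift from baseline in terms of low/normal/high for hematology and serum chemistry tests", and also a normal/abnormal shift. It adds that "Actual results and changes from Baseline in clinical hematology and serum chemistry will be summarized by treatment within each cohort" and time point, and it lists all laboratory data. SAP section 4 gives the summary statistics as n, mean, median, SD, minimum and maximum. No graded shift table, and no count of children crossing a worsening threshold, is planned.

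**When blood is drawn.** Protocol Appendix 1 schedules safety laboratory tests at Screening and at 24 hours after dosing only.

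**The concern.** Safety is the secondary objective. Every child is hospitalized with a suspected or confirmed infection, and no eligibility criterion in Protocol 6.2 sets a numeric laboratory limit. Abnormal baseline values are therefore foreseeable, and the illness offers a ready explanation for further change.

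A three-level shift works for a child who starts normal. It says nothing about how far a child who starts abnormal moves in the same direction. Protocol 8.14.4 relies on the laboratory analyses for changes not recorded as AEs, so the weakness of the shift table and the expectedness condition can coincide in the same child. A reader who takes the incidence and shift tables as the count of children whose laboratory values worsened would miss that child.

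**Working it through.** The plan states no figure on this point, so there is none to reproduce. The cell size is 10 per treatment per age cohort (Protocol 12.2, SAP 4.1); 2 treatments × 2 cohorts × 10 = 40, as stated.

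**Step 1. Where a scheduled 24-hour result is counted.**
- Normal at Baseline, abnormal at 24 hours: a shift in both tables.
- Low to high, or high to low: a shift in the low/normal/high table.
- Already abnormal, further in the same direction, clinically significant and not expected: an AE under 8.14.4, which meets the TEAE definition.
- The same, but part of another AE diagnosis: counted under that diagnosis.
- Already abnormal, further in the same direction, clinically significant but judged expected, and not part of another diagnosis: not an AE and no shift. It enters the change-from-Baseline summary and the listing only.

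The last line is the gap.

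**Step 2. What each summary shows.** Values are assumed, in multiples of the upper limit of normal. In a cell of 10, one child starts at 2.0 and nine stay at 0.6. The one child rises to 3, 5 or 8.

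| Rises to | Shift table | Mean change | SD of change | Median change | Maximum change |
|---|---|---|---|---|---|
| 3 | 1 High-to-High, 9 Normal-to-Normal | 1/10 = 0.1 | 0.32 | 0 | 1.0 |
| 5 | identical | 3/10 = 0.3 | 0.95 | 0 | 3.0 |
| 8 | identical | 6/10 = 0.6 | 1.90 | 0 | 6.0 |

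The shift table does not distinguish the three cases. The change summary does, through the mean, SD and maximum. By contrast, a child going from 0.8 to 3.0 appears as Normal-to-High.

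**Step 3. Size within one cell.** Let q be the share already abnormal in the relevant direction; the documents do not give it. Then m = 10 × (1 − q) children can still shift in that direction. Assume the effect occurs in 10% of children independently and is large enough to take a normal value across the limit. Then P(at least one shift) = 1 − 0.9^m.
- q = 0: m = 10, 1 − 0.349 = 65%
- q = 20%: m = 8, 1 − 0.430 = 57%
- q = 50%: m = 5, 1 − 0.590 = 41%

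**Step 4. The same assumptions over all four cells.**
- q = 0: 40 children, 1 − 0.9^40 = 98.5%
- q = 20%: 32 children, 1 − 0.9^32 = 97%
- q = 50%: 20 children, 1 − 0.9^20 = 88%

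The loss is marked within a cell and modest over the whole study.

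**The case against.** The strongest reply is that little is hidden. With about 40 children and one scheduled post-dose draw each, all laboratory data are listed. A rise from 1.2 to 8 times the upper limit in one child of 10 moves the mean change by 6.8/10 = 0.68 and sets the maximum. Protocol 12.5 has the sponsor review laboratory results as each child completes. Protocol 8.14.4 also judges a value against that child's own Baseline, so a rise that large would be hard to call expected and should be recorded as an AE.

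Most of this stands, and it rules out three stronger readings that a reader might infer.
- *Post-dose worsening in sick children drops out of every incidence table.* It does not. Step 1 shows four routes by which worsening is counted.
- *The safety results are biased towards no effect.* The documents do not support this. There is no control arm, Protocol 12.10 plans no formal comparisons, and the change summaries register the same events.
- *The expectedness condition is a causal judgement that contradicts the AE definition and must be deleted.* Asking whether a value is expected is not the same as asking whether the drug caused it. Deleting the condition could turn the infection's own laboratory course into AEs. Still, Protocol 8.3 and 8.9 contain no exception for expected worsening, so the three sections sit awkwardly together.

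The reply leaves the counting gap open. A maximum or a listing is not a count of children, and sponsor review has no stated laboratory threshold. Change summaries in raw units also pool local laboratories from about 15 sites, a poorer basis for judging size than multiples of each laboratory's own limit. SAP section 4 keeps unscheduled results out of the summary tables except to set Baseline. For worsening seen only after the 24-hour draw, an AE record is therefore the one planned route into a summary table.

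**Conclusion.** The point holds in a limited form. The SAP 9.2 shift tables cannot show same-direction worsening from an abnormal Baseline. If the investigator also judges that change expected under Protocol 8.14.4, and it is not part of another AE diagnosis, no planned incidence or shift category counts it. Scheduled results remain visible in the change-from-Baseline summaries and the listings.

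The table defect follows from its categories and needs no assumption. Its size is unknown. The fall from 65% to between 57% and 41% is for a single cell of 10 and rests on assumed abnormal-baseline shares of 20% to 50% and an assumed 10% effect rate. Neither is an estimate for this population. This is a low-cost improvement to safety reporting and does not put the study's conclusions in doubt.

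**What to change.** **SAP 9.2.** For liver enzymes, total bilirubin, CK, amylase and lipase, report the shift from Baseline in pre-specified bands of multiples of the local upper limit of normal, for example ≤1, >1–3, >3–5 and >5. The bands are illustrative and come from neither document; the sponsor should fix them in the SAP before database lock. In the Step 2 example, the rises to 5 and to 8 would each show as a shift to a different band. The rise to 3 would stay within >1–3, so the table is finer but still has limits.

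**Cost.** One revised table. Protocol 13.8 already requires normal values and units from each laboratory, and no new samples or subjects are needed. The table is larger and sparser: 4 × 4 = 16 entries per test instead of 3 × 3 = 9, with 10 children per cell. Bands above the upper limit do not help with tests where the concern is a fall, nor with unscheduled results.

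**Protocol.** Separately, the sponsor should reconcile the expectedness condition in 8.14.4 with 8.3 and 8.9, so that sites apply one recording rule. Which rule applies is for the sponsor to decide. Any change to the protocol text needs an amendment with sponsor and IRB/IEC/REB approval under Protocol 13.6.2; the SAP table does not depend on it.
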